6.4. Changes From Protocol-Specified Efficacy Analyses

There are no changes from protocol-specified efficacy analyses.

7. SAFETY ANALYSES

7.1. Adverse Events and Deaths

7.1.1. Adverse Event Dictionary

Clinical and laboratory adverse events (AEs) will be coded using Medical Dictionary for Regulatory Activities (MedDRA). System organ class (SOC), high-level group term (HLGT), high-level term (HLT), preferred term (PT), and lower-level term (LLT) will be provided in the AE dataset.

7.1.2. Adverse Event Severity

Adverse events are graded by the investigator as Grade 1, 2, 3, or 4 according to toxicity criteria specified in the protocol. The severity grade of events for which the investigator did not record severity will be categorized as “missing” for tabular summaries and data listings and the most severe will be considered (for sorting purpose only) in data presentation.

7.1.3. Relationship of Adverse Events to Study Drug

Related AEs are those for which the investigator selected “Related” on the AE eCRF to the question of “Related to Study Treatment”. Events for which the investigator did not record relationships to study drug will be considered related to study drug for summary purposes. However, by-subject data listings will show the relationship as missing from that captured on the CRF.

7.1.4. Serious Adverse Events

Serious adverse events (SAEs) will be identified and captured as SAEs if AEs met the definitions of SAE specified in the study protocol. Serious adverse events captured and stored in the clinical database will be reconciled with the SAE database from the Gilead Pharmacovigilance and Epidemiology Department before database finalization.

7.1.5. Treatment-Emergent Adverse Events

7.1.5.1. Definition of Treatment Emergent

Treatment-emergent adverse events (TEAEs) are defined as one or both of the following:

- Any AEs with an onset date on or after the study drug start date and no later than 30 days after permanent discontinuation of study drug.
- Any AEs leading to premature discontinuation of study drug.

7.1.5.2. Incomplete Dates

If the onset date of the AE is incomplete, then the month and year (or year alone if month is not recorded) of onset determine whether an AE is treatment emergent, as long as the AE stop date is not prior to the first dose date of study drug. The event is considered treatment emergent if both of the following 2 criteria are met:

- The AE onset and end dates are the same as or after the month and year (or year) of the first dose date of study drug
- The AE onset date is the same as or before the month and year (or year) of the 30th day after the date of the last dose of study drug

An AE with completely missing onset and stop dates, or with the onset date missing and a stop date later than the first dose date of study drug, will be considered to be treatment emergent.

7.1.6. Summaries of Adverse Events and Deaths

A brief high-level summary of TEAEs will be provided by presenting the number and percentage of subjects who had the following: any AE; any AE of Grade 3 or above; any AE of Grade 2 or above; any treatment-related AE; any treatment-related AE of Grade 3 or above; any treatment-related AE of Grade 2 or above; any SAE; any treatment-related SAE; any AE that led to premature discontinuation of SOF/VEL/VOX; any AE that led to interruption of SOF/VEL/VOX. All deaths (including those that are treatment emergent and those that are not treatment emergent) observed during the study will also be summarized and included in this table.

Adverse event summaries will provide the number and percentage of subjects with TEAEs by SOC and PT, based on the Safety Analysis Set as follows:

- All AEs
- AEs of Grade 3 or above
- AEs of Grade 2 or above
- All treatment-related AEs
- Treatment-related AEs of Grade 3 or above
- Treatment-related AEs of Grade 2 or above
- All SAEs
- All treatment-related SAEs

- AEs leading to premature discontinuation of SOF/VEL/VOX
- AEs leading to interruption of SOF/VEL/VOX

Multiple events will be counted only once per subject in each summary. Adverse events will be summarized and listed first in alphabetic order of SOC and then by PT in order of descending incidence overall within each SOC. In summaries by severity grade, the most severe grade will be used for those AEs that occurred more than once in an individual subject during the study.

In addition to the above summary tables, TEAEs will be summarized by PT only, in order of descending incidence for:

- AEs that occurred in at least 5% of subjects within this age group
- AEs of Grade 3 or above
- All treatment-related AEs
- All SAEs
- AEs leading to premature discontinuation of SOF/VEL/VOX
- AEs leading to interruption of SOF/VEL/VOX

In addition to the summaries described above, data listings will be provided for the following:

- All AEs (with a variable indicating whether the event is treatment emergent)
- AEs of Grade 3 or above
- SAEs
- Deaths
- AEs leading to premature discontinuation of SOF/VEL/VOX
- AEs leading to interruption of SOF/VEL/VOX

7.2. Laboratory Evaluations

Laboratory data collected during the study will be analyzed and summarized using both quantitative and qualitative methods. Summaries of laboratory data will be provided for the Safety Analysis Set and will include data collected up to the last dose of study drug plus 30 days for subjects who have permanently discontinued study drug. The analysis will be based on values reported in conventional units. When values are below the limit of quantitation, they will be listed as such, and the closest imputed value will be used for the purpose of calculating summary statistics. For example, if “< 0.2” was recorded, a value of 0.1 will be used for the purpose of calculating summary statistics; if “< 0.1” was recorded, a value of 0.09 will be used for the purpose of calculating summary statistics.

A by-subject listing for laboratory test results will be provided by subject ID number and visit in chronological order for hematology, serum chemistry, and urinalysis separately. Values falling outside of the relevant reference range and/or having a severity grade of 1 or higher on the Gilead Grading Scale for Severity of Adverse Events and Laboratory Abnormalities will be flagged in the data listings, as appropriate.

No inferential statistics will be generated.

7.2.1. Summaries of Numeric Laboratory Results

Descriptive statistics (n, mean, SD, median, Q1, Q3, minimum, and maximum) will be provided for ALT, aspartate aminotransferase (AST), total bilirubin, alkaline phosphatase, hemoglobin, reticulocytes, white blood cell (WBC), neutrophils, lymphocytes, platelets, and international normalized ratio (INR) as follows:

- Baseline values
- Values at each postbaseline analysis window
- Change from baseline at each postbaseline analysis window

A baseline laboratory value will be defined as the final assessment performed on or prior to the date/time of first dose of study drug. Change from baseline to a postbaseline visit will be defined as the visit value minus the baseline value. The mean, median, Q1, Q3, minimum, and maximum will be displayed to the reported number of digits; SD to the reported number of digits plus 1.

Median (Q1, Q3) of the observed values for these laboratory parameters will be plotted using a line plot by visit.

In the case of multiple values in an analysis window, data will be selected for analysis as described in Section 3.7.3 (Selection of Data in the Event of Multiple Records in a Window).

The number of subjects with hemoglobin < 10 g/dL and < 8.5 g/dL at any postbaseline visits (up to 30 days after the last dose of any study drug) will be summarized.

7.2.2. Graded Laboratory Values

The Gilead Grading Scale for Severity of Adverse Events and Laboratory Abnormalities will be used for assigning toxicity grades to laboratory results for analysis as Grade 0, Grade 1, Grade 2, Grade 3, or Grade 4. Grade 0 includes all values that do not meet the criteria for an abnormality of at least Grade 1. Some laboratory tests have criteria for both increased and decreased levels; analyses for each direction (ie, increased, decreased) will be presented separately.

7.2.2.1. Treatment-Emergent Laboratory Abnormalities

Treatment-emergent laboratory abnormalities are defined as values that increase at least 1 toxicity grade from baseline at any postbaseline time point, up to and including the date of last dose of study drug plus 30 days for subjects who permanently discontinued study drug. If the relevant baseline laboratory value is missing, then any abnormality of at least Grade 1 will be considered treatment emergent.

7.2.2.2. Summaries of Laboratory Abnormalities

Laboratory data that are categorical will be summarized using the number and percentage of subjects in the study with the given response at baseline and each scheduled postbaseline visit.

The following summaries (number and percentage of subjects) for treatment-emergent laboratory abnormalities will be provided by analyte; subjects will be categorized according to the most severe postbaseline abnormality grade for a given analyte:

- Graded laboratory abnormalities
- Grade 3 or above laboratory abnormalities

For all summaries of laboratory abnormalities, the denominator is the number of subjects with nonmissing postbaseline values up to 30 days after last dose for the laboratory parameter of interest.

A by-subject listing of treatment-emergent Grade 3 or above laboratory abnormalities will be provided by subject ID number and visit in chronological order. This listing will include all test results that were collected throughout the study for the analyte of interest, with all applicable severity grades or abnormal flags displayed.

For subjects with at least one event of treatment-emergent Grade 3 or above laboratory abnormality of creatine kinase (CK) or lipase, a listing of AEs will be provided.

7.2.2.3. On-Treatment Liver-Related Laboratory Events

The following liver-related laboratory events will be summarized using data from all the on-treatment postbaseline visits (up to 3 days after the last dose of any study drug):

- $AST \text{ or } ALT > 3 \times ULN$ and $\text{total bilirubin} > 2 \times ULN$
- $ALT > 5 \times ULN$
- $\text{Total bilirubin} > 2 \times ULN$

For the composite criterion of AST or ALT and total bilirubin, AST or ALT and total bilirubin must meet the specified cut-offs at a given postbaseline time point; subjects will be counted once when the criterion is met. The denominator will be the number of subjects in the Safety Analysis

Set with at least 1 postbaseline value of AST or ALT and total bilirubin at the same time point. For individual laboratory tests, subjects will be counted once based on the most severe postbaseline values when the criterion is met. The denominator will be the number of subjects in the Safety Analysis Set with at least 1 nonmissing postbaseline value for the test. A listing will be provided including ALT, AST, total bilirubin, direct bilirubin, alkaline phosphatase, HCV RNA (\log_{10}) and yes/no flag for subjects meeting at least 1 of the 3 criteria. All the available data for the subjects will be listed.

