3.5. Discontinuation Criteria

The medical monitor should be consulted prior to subject discontinuation when medically feasible. Study medication must be discontinued in the following instances:

- Intercurrent illness that would, in the judgment of the investigator, affect assessments of clinical status to a significant degree. Following resolution of intercurrent illness, the subject may resume study dosing at the discretion of the investigator
- Unacceptable toxicity (as defined in Section 7.5 of the protocol) or toxicity that, in the judgment of the investigator, compromises the ability to continue study-specific procedures or is considered to not be in the subject's best interest
- Pregnancy of female subject or female partner of male subject
- Efficacy failure as defined in Section 3.4
- Significant protocol violation including non-compliance with study assessments
- Subject or parent/legal guardian request to discontinue for any reason; it is important to determine whether the withdrawal of consent is primarily due to an AE, lack of efficacy, or other reason
- Discontinuation of the study at the request of Gilead, regulatory agency, or an Independent Ethics Committee (IEC)

Subjects who meet any of the following criteria must stop treatment with SOF/VEL/VOX FDC:

- Elevation of ALT and/or AST above the upper limit of normal and $> 5x$ Day 1 or nadir, confirmed by immediate repeat testing
- Elevation of ALT $> 3x$ Day 1 and total bilirubin $> 2x$ ULN, confirmed by immediate repeat testing
- Any Grade 3 or greater rash associated with constitutional symptoms (see Appendix 3)
- Any Grade 4 adverse event assessed as related to administration of SOF/VEL/VOX FDC (see Appendix 3)

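### The SAP's liver-event table uses fixed ULN multiples only, so it can count a falling pre-existing elevation and can miss some ALT/AST flares that meet the protocol's Day 1/nadir criterion

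*SAP*

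**What the plan says.** SAP 7.2.2.3 introduces its table with "The following liver-related laboratory events will be summarized using data from all the on-treatment postbaseline visits", and takes values up to 3 days after the last dose. It defines three on-treatment liver events:

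- AST or ALT above 3 x ULN together with total bilirubin above 2 x ULN at the same time point;
- ALT above 5 x ULN;
- total bilirubin above 2 x ULN.

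None refers to Day 1 or nadir, and there is no row for AST alone. For the single-test rows, "subjects will be counted once based on the most severe postbaseline values when the criterion is met". A listing supports the table: "All the available data for the subjects will be listed", but it covers only subjects who meet at least one of the three criteria.

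Protocol 3.5 has two hepatic stopping criteria based on laboratory values. The first is "Elevation of ALT and/or AST above the upper limit of normal and $> 5x$ Day 1 or nadir, confirmed by immediate repeat testing". The second is ALT above 3 times Day 1 with total bilirubin above 2 x ULN, also confirmed. Protocol 4.3 excludes ALT or AST only when above 10 x ULN at Screening.

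The baseline-referenced summary of abnormalities is in SAP 7.2.2.1, where treatment-emergent means "values that increase at least 1 toxicity grade from baseline at any postbaseline time point". It refers to baseline, not nadir. No summary in the SAP counts subjects who met the protocol 3.5 hepatic criteria.

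**The concern.** The SAP itself allows for raised ALT at baseline and a return to normal: it categorises baseline ALT at 1.5 x ULN (3.4, 5.2) and plans an ALT normalization analysis (6.2.1). In such subjects, an on-treatment value above a ULN cut-off may be only what remains of the Day 1 elevation. The informative hepatic signal is a rise from Day 1 or nadir, which is how protocol 3.5 frames it.

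A table without that reference can go wrong in both directions. It can report an event in a subject who is improving, and leave out one whose values met the protocol's own flare criterion. Safety is a secondary objective and the cohort is small, so one subject on the wrong side of the line changes the reported rate visibly.

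**Working it through.** The documents give no figure for this table, so there is none to reproduce. The check applies three sets of rules to the same values, all in multiples of ULN: the SAP 7.2.2.3 rows, the protocol 3.5 criteria, and the protocol Appendix 3 ALT/AST grades (Grade 1: 1.25 to 2.5; Grade 2: above 2.5 to 5; Grade 3: above 5 to 10; Grade 4: above 10). The trajectories are illustrative.

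**Falling elevations.** A subject with Day 1 ALT of b (b above 5) is counted in the ALT row unless ALT has fallen by at least 1 − 5/b by the first on-treatment sample (Week 1):

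- b = 6: 1 − 5/6 = 16.7%
- b = 8: 1 − 5/8 = 37.5%
- b = 10: 1 − 5/10 = 50%

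Similarly, ALT falling from 8 to 4 with total bilirubin above 2 x ULN enters the composite row, although ALT has halved.

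**First protocol criterion, ALT.** With reference r (Day 1 or nadir), the criterion applies above max(1, 5r), while the SAP row counts only above 5. The missed band runs from max(1, 5r) to 5 and exists only when r is below 1:

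- r = 0.3: 1.5 to 5
- r = 0.5: 2.5 to 5
- r = 0.8: 4 to 5
- r = 1 or more: none

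**First protocol criterion, AST only.** With no AST row, such a flare is missed at any height unless total bilirubin is also above 2 x ULN.

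**Second protocol criterion.** Every case has total bilirubin above 2 x ULN, so it is in the bilirubin row and the listing. It is absent from the composite row when ALT and AST are both at or below 3, for example ALT 0.5 to 1.8 (1.8/0.5 = 3.6 times Day 1).

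**What the graded table adds.** For ALT:

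| Day 1 | Nadir | Later value | Ratio | Meets first criterion if confirmed | Counted in ALT > 5 x ULN | Grade, Day 1 to later | Treatment-emergent |
|---|---|---|---|---|---|---|---|
| 8 | – | 6 | 6/8 = 0.75 | no | yes | 3 to 3 | no |
| 0.5 | 0.5 | 3.0 | 3.0/0.5 = 6 | yes | no | 0 to 2 | yes |
| 1.0 | 1.0 | 6.0 | 6.0/1.0 = 6 | yes | yes | 0 to 3 | yes |
| 3.0 | 0.5 | 4.5 | 4.5/0.5 = 9 | yes | no | 2 to 2 | no |

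A rise to more than 5 times Day 1 that reaches 1.25 x ULN always moves up at least one grade, for Day 1 values up to 10 x ULN. From Grade 0 it reaches Grade 1 or higher; from 1.25 it exceeds 6.25 (Grade 3); from just above 2.5 it exceeds 12.5 (Grade 4); from Grade 3 it exceeds 25 (Grade 4). The graded table therefore picks up flares measured from Day 1, though without identifying them as having met the criterion. The gap common to both tables is the rebound from nadir, as in the last row. That subject is also outside the 7.2.2.3 listing and the Grade 3-or-above listing in SAP 7.2.2.2.

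**Size.** One subject in 20 is 1/20 = 5 percentage points.

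**The case against.** The strongest reply is that this is a descriptive ULN screen which protocol 8.6.3 does not require, that nothing obliges it to copy individual stopping rules, and that the information is available elsewhere. Much of that stands:

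- Protocol 7.1.3 requires an adverse event record when a laboratory abnormality leads to interruption, modification or discontinuation of study drug. SAP 7.1.6 tabulates and lists adverse events leading to interruption or discontinuation.
- SAP 7.2 lists all laboratory results by subject and visit, with out-of-range and graded values flagged.
- SAP 7.2.1 gives change from baseline for ALT and AST, and SAP 7.2.2.1 compares grades with baseline.
- A subject who enters high and is still above 5 x ULN at Week 1 is in the 7.2.2.3 listing with all data shown, so a later rebound in that subject is displayed.
- The analysis covers only adolescents who are DAA-naive without cirrhosis (SAP 2.2, 3.2). Protocol 1.1 places abnormal transaminases particularly in the first 2 years of life. Nothing shows that any analysed subject entered above 5 x ULN.

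These points narrow the concern without closing it. Change from baseline is a group summary by visit, the graded table never looks at nadir, and the full listing leaves the reader to calculate ratios by hand. The mandatory adverse event record depends on dosing having been changed. A flare first seen at the Week 8 End of Treatment visit has no remaining dosing to stop and, without signs, symptoms or intervention, need not be recorded.

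**Conclusion.** The concern holds in a limited form. The table can count a falling pre-existing elevation. It can miss an ALT flare from a reference below ULN that peaks at or below 5 x ULN, and an AST-only flare without raised bilirubin. Among these, a nadir rebound that stays within the baseline grade is also outside the treatment-emergent table.

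A reader might infer that the table misses Day 1/nadir flares in general. The documents do not support that: an ALT flare from a reference at or above ULN exceeds 5 x ULN and is counted, and every case under the ALT-with-bilirubin criterion reaches the bilirubin row and the listing. Nor would a missed flare be invisible; the full laboratory listing holds it, and if it led to stopping it must be an adverse event.

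How many subjects are affected cannot be computed, because no baseline ALT distribution is given. The figure of 5 percentage points per subject assumes 20 subjects. The trajectories are illustrative, and each flare is a protocol 3.5 event only if confirmed on repeat testing. The change is worth making because the SAP otherwise has no count of subjects who met the hepatic criteria on which the protocol acts.

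**What to change.** In SAP 7.2.2.3:

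1. Keep the three ULN rows. Split them by Day 1 ALT/AST category (for example, at or below versus above the row's cut-off), or show whether the counted value exceeds Day 1.
2. Remove no subject from the composite row. Requiring ALT to exceed Day 1 would drop a subject whose ALT goes from 8 to 7 x ULN while total bilirubin newly rises above 2 x ULN.
3. Add summary rows and a listing for subjects whose values meet each existing protocol 3.5 hepatic laboratory criterion, covering AST as well as ALT and nadir as well as Day 1, with a flag for confirmation on repeat testing.

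This changes no clinical threshold and needs no new data. The cost is SAP wording, some programming and a slightly longer table. If the SAP is not reopened, its section 1 already provides for later changes to be documented in the clinical study report.

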8.6. Safety Analysis

Safety will be evaluated by assessment of clinical laboratory tests, physical examinations, vital signs measurements at various time points during the study, and by the documentation of AEs.

All safety data collected on or after the first dose of the study drug administration up to 30 days after the last dose of the study drug will be summarized by age cohort and treatment duration (8 weeks vs 12 weeks) according to the study drug taken.

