8.6.3. Laboratory Evaluations

Selected laboratory data (using conventional units) will be summarized (n, mean, SD, median, Q1, Q3, minimum, and maximum) by study visit along with the corresponding change from baseline.

Graded laboratory abnormalities will be defined using the laboratory toxicity grading scheme defined in [Appendix 3](#).

Incidence of treatment-emergent laboratory abnormalities, defined as values that increase by at least one toxicity grade from baseline at any time post baseline up to and including the date of last dose of study drug plus 30 days, will be summarized by age cohort and treatment duration (8 weeks vs 12 weeks).

Values for missing safety laboratory data will not be imputed; however, a missing Day 1 result will be replaced with a screening result, if available. If no pretreatment laboratory value is available, the baseline value will be assumed to be normal (ie, no grade [Grade 0]) for the summary of graded laboratory abnormalities.

All laboratory abnormalities will be included in the listings of laboratory data.

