7.11. Changes From Protocol-Specified Safety Analyses

There are no deviations from the protocol-specified safety analyses.

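### The combined AST/ALT and bilirubin criterion is evaluated only to 3 days after last dose, and no SAP display applies it to days 4 to 30 of the protocol's treatment-emergent period

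*SAP*

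**What the plan says.** SAP 7.2.2.3, whose title restricts it to on-treatment events, defines the three liver criteria and has them "summarized using data from all the on-treatment postbaseline visits (up to 3 days after the last dose of any study drug". For the combined criterion, both analytes must exceed their cut-offs at the same time point. A listing accompanies the table for subjects who meet at least one of the three criteria, and it shows all available data for them.

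The 3-day limit is the SAP's general boundary between on-treatment and posttreatment data (SAP 3.7.2).

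The other safety windows are longer:

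- Protocol 8.6: safety data "up to 30 days after the last dose of the study drug will be summarized by age cohort and treatment duration". Protocol 8.2.1.2 defines treatment-emergent data over the same period.
- Protocol 8.6.3: treatment-emergent laboratory abnormalities are those arising "at any time post baseline up to and including the date of last dose of study drug plus 30 days".
- SAP 7.2: laboratory summaries "will include data collected up to the last dose of study drug plus 30 days for subjects who have permanently discontinued study drug".
- SAP 7.2.2.1: treatment-emergent abnormalities run "up to and including the date of last dose of study drug plus 30 days".
- SAP 7.2.2.2: for the abnormality tables, which are by analyte, "the denominator is the number of subjects with nonmissing postbaseline values up to 30 days after last dose for the laboratory parameter of interest".
- SAP 7.2.1: the count of subjects with hemoglobin below 10 and below 8.5 g/dL also runs to 30 days.

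SAP 7.11 states: "There are no deviations from the protocol-specified safety analyses".

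**The concern.** SAP 7.2.2.3 is the only place where transaminases and bilirubin are read together. The graded tables take one analyte at a time, so they cannot show that two elevations coincided. If the combined criterion is first met after day 3, the table can report zero combined events although one occurred inside the period that the protocol treats as treatment-emergent. The SAP gives no reason for following hemoglobin thresholds to 30 days and liver thresholds to 3.

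The limit is also tied to last dose, and Protocol 3.5 ends dosing on certain liver test results. A subject stopped on a transaminase rise may therefore leave the table's window shortly after the stop, before any later bilirubin rise is sampled.

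**Working it through.** The plan states no figure for this table, so the check compares windows, maps cut-offs to grades and counts days.

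**1. Displays that cover days 4 to 30 after last dose**

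| Display | Covers days 4 to 30? | Combined criterion? |
|---|---|---|
| Liver-event table, SAP 7.2.2.3 | No | Yes |
| Liver listing, SAP 7.2.2.3 | Yes, for subjects who met a criterion in the table's window | Flag follows the table |
| Graded tables and Grade 3 or above listing, SAP 7.2.2.1 and 7.2.2.2 | Yes | No, single analyte |
| Numeric summaries, SAP 7.2.1, with the FU 4 window of days 4 to 30 in SAP Table 3-2 | Yes | No, single analyte |
| General laboratory listing, SAP 7.2 | Yes | No, flags single values |

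The liver listing sentence does not repeat the 3-day limit. I take its criteria to be those just defined in the same section.

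**2. Days and scheduled data outside the table**

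- Days excluded within the 30-day period: 30 − 3 = 27 (days 4 to 30).
- The 4-week posttreatment chemistry (Protocol Appendix Table 2) may be drawn at 28 ± 5 days, so days 23 to 33, which is 33 − 23 + 1 = 11 permitted days.
- Permitted days inside the 3-day limit: 0 of 11.
- Permitted days inside a 30-day limit: days 23 to 30, so 8 of 11. Days 31 to 33 are in tolerance for the visit but beyond both the 30-day limit and the FU 4 safety-laboratory window.

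**3. Whether the graded tables stand in for the criteria (Protocol Appendix 3)**

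- ALT and AST: Grade 2 is above 2.50 to 5.00 x ULN; Grade 3 starts above 5.00 x ULN.
- Bilirubin: Grade 2 is above 1.5 to 2.5 x ULN; Grade 3 starts above 2.5 x ULN.
- ALT above 5 x ULN is therefore Grade 3 or above, and is counted to 30 days if it is a rise of at least one grade from baseline.
- Bilirubin above 2 x ULN falls inside the Grade 2 band, so no graded table isolates it.
- ALT or AST above 3 to 5 x ULN with bilirubin above 2 to 2.5 x ULN is Grade 2 on both analytes. It meets the combined criterion but does not reach the Grade 3 or above listing.

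**4. Hypothetical case**

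- At last dose: ALT 4 x ULN, bilirubin 1.6 x ULN. No liver criterion is met. Both analytes are Grade 2.
- After day 3 (an unscheduled draw on day 6, or the scheduled draw on day 28): ALT 4 x ULN, bilirubin 2.4 x ULN. The combined criterion and the bilirubin criterion are both met. Both analytes are still Grade 2.
- The liver table is unchanged, the subject does not enter the liver listing, the worst grade is unchanged, and the Grade 3 or above listing is not triggered. Flags on the separate values in the general laboratory listing remain.

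**5. Subjects stopped under the liver rules in Protocol 3.5** (analysis consequence only; no view is taken on the rules)

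- Relative rule: above ULN and above 5 times the Day 1 or nadir value. With a reference value of r x ULN, it is met above max(1, 5r) x ULN. At r = 0.3 this is 1.5; at 0.5 it is 2.5; at 0.8 it is 4.0; at 1.0 it is 5.0.
- For ALT with r of at least 1.0, the stop implies ALT above 5 x ULN, which meets the second liver criterion. With r below 1.0 the subject may meet none. A stop on AST alone does not meet the second criterion either, because that criterion uses ALT only.
- Combined stopping rule: it requires bilirubin above 2 x ULN. If that sample falls by day 3, the third liver criterion is met, so the subject is counted and all later data are listed.

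**6. Scale**

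With the minimum cohort of 20, no event gives 0/20 = 0% (exact 95% CI 0 to 16.8%). One event gives 1/20 = 5% (0.1 to 24.9%).

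**The case against.** The strongest case against is that nothing is broken. The protocol asks for graded treatment-emergent laboratory summaries to 30 days, and the SAP supplies them. The liver-event table is an SAP addition. Its title says on-treatment, and its limit matches the SAP's own definition of on-treatment data. All of that stands. A reader might infer a breach of Protocol 8.6 or a contradiction of SAP 7.11, but a supplementary on-treatment table beside the 30-day summaries is neither.

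A reader might also infer that late liver abnormalities go unflagged. The documents do not support that. The general laboratory listing flags every out-of-range or graded value, ALT, AST and bilirubin are graded to 30 days, and the FU 4 numeric summary shows maxima. A subject who met any criterion by day 3 has all later data in the liver listing. Protocol 7.1.3 further requires a laboratory abnormality that leads to discontinuation to be recorded as an adverse event, and SAP 7.1.6 tabulates and lists those, so a hepatic stop is reported in any case.

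A third tempting reading is that the table generally loses the subjects who stop for liver reasons. Step 5 shows that many such subjects would already meet the second or third criterion. The loss is limited to relative-rule stops with a reference value below ULN, stops on AST alone, and elevations that begin after treatment.

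The 27 days also overstate the volume of data: only one scheduled chemistry falls in them. These points narrow the finding. They do not supply a 30-day count of the combined criterion.

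**Conclusion.** The narrow point holds. For days 4 to 30 after last dose, no SAP display counts the combined AST/ALT and bilirubin criterion, or bilirubin above 2 x ULN, and meeting either for the first time in that period does not bring the subject into the liver listing. The clearest exposure is an event that is Grade 2 on both analytes, because the Grade 3 or above listing does not pick it up either. A reported zero would be correct for the on-treatment period and could be wrong for the protocol's treatment-emergent period.

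The consequence is modest. The analysis is descriptive, and no primary or key efficacy endpoint is affected. A careful reader of the by-subject laboratory listing could reconstruct a late combined event. The 0% versus 5% contrast is for scale only: it assumes 20 subjects and one event, and the documents give no expected rate. The conclusion on the listing assumes that its criteria carry the table's 3-day limit. This is a cheap improvement to coverage, not the correction of an error.

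**What to change.** In SAP 7.2.2.3, keep the on-treatment row and add a row for the same three criteria through last dose plus 30 days, with the denominator defined over the same window. Let a criterion met at any time in that window bring the subject into the liver listing, with the flag showing whether it was met on treatment or afterwards. State how 4-week posttreatment chemistries drawn on days 31 to 33 are handled, since a 30-day limit covers 8 of the 11 permitted days and leaves those three out.

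The cost is a sentence or two in the SAP and an extra row in an existing table. The data are already collected, and SAP Table 3-2 already windows safety laboratory data for days 4 to 30. The downside is that some posttreatment elevations unrelated to drug will be counted; the separate on-treatment row distinguishes them.
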